8.7 Vital Signs

Vital signs include temperature, heart rate, respiration rate, pulse oximetry, and blood pressure. Collection should occur after the patient has been sitting for 3-5 minutes.

8.8 Electrocardiograms

All patients will have a 12-lead ECG performed at the screening visit and pre-treatment visit (Study Day 0 or 1), as well as Day 21 (± 3 days), and Day 28 (± 3 days) only if delayed end of cycle) of each cycle. During the days when patients are undergoing PK sampling (during Cycle 1, infusions 1 and 5; Cycle 3, infusions 1 and 5), an ECG will be performed at 3 distinct time points (triplicates) within 5 minutes prior to each PK sample collection pre-infusion and at 30 and 60 minutes post-infusion (see [Table 9](#) in [Section 9.8](#)). An ECG should be performed after patient is supine for 5 minutes. All ECGs will be analyzed by a central facility.

8.9 Clinical Laboratory Tests

The following assessments should be done per the visit schedule and processed by the local laboratory:

- Hematology: Minimally, scheduled hematology collections should include white blood cell (WBC) count, differential white cell count (lymphocytes, monocytes, basophils, eosinophils, neutrophils), red blood cell (RBC) count, hematocrit, hemoglobin and platelet count.
- Serum albumin: May be a component of the serum chemistry panel. See [Appendix E](#) for management of changes in albumin values.
- Serum electrolytes and chemistry: Sodium, potassium, bicarbonate, chloride, blood urea nitrogen (BUN), creatinine, glucose, ALT, albumin, ALP, AST, bilirubin (total, direct, and indirect), calcium, CPK, magnesium, LDH, phosphate, total protein, and uric acid.
- Coagulation parameters: PT and/or INR, aPTT.
- Urinalysis: Appearance, color, pH, specific gravity, ketones, leukocytes, protein, glucose, bilirubin, urobilinogen, and occult blood.

8.10 Urine or Serum Pregnancy Test

A urine or serum pregnancy test will be performed within 1 week prior to treatment for WOCBP who are not on acceptable birth control measures. The pregnancy test should be performed at the clinical research site and processed by the local laboratory.

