3. The patient \geq 18 years old.
4. The patient has an Eastern Cooperative Oncology Group (ECOG) performance status (PS) of 0-2.
5. The patient has adequate baseline organ function, including cardiac, renal, and hepatic function:
 - LVEF \geq institutional lower limit of normal as measured by multigated acquisition (MUGA) scan or 2-dimensional (2-D) echocardiography (ECHO) within 28 days prior to start of therapy and no clinically significant abnormalities on a 12-lead electrocardiogram (ECG)
 - Serum creatinine \leq 1.5 mg/dL (133 μ mol/L)
 - Serum albumin \geq 3.2 g/dL (32 g/L) (please note that albumin infusions are not permitted in order to enable eligibility)
 - Bilirubin \leq 1.5 mg/dL (26 μ mol/L)
 - AST and ALT \leq 2.5 times the upper limit of normal (ULN)

6. If the patient is a woman of child bearing potential (WOCBP), she has had a negative serum or urine pregnancy test within 1 week prior to treatment.
7. The patient has signed informed consent prior to initiation of any study-specific procedures or treatment.
8. The patient is able to adhere to the study visit schedule and other protocol requirements, including follow-up for survival assessment.
9. The patient (male and female) agrees to use acceptable contraceptive methods for the duration of time on the study, and continue to use acceptable contraceptive methods for 2 months after the last infusion of SL-401.

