8.1 Patient Selection

Patients with BPDCN or R/R AML who have previously received at least one line of therapy for their disease, previously untreated AML that is considered high risk for disease progression, and who otherwise meet the inclusion/exclusion criteria will be recruited for enrollment into the study. Patients will be advised of the clinical protocol by the Investigator. If the patient is interested and is potentially eligible for participation in the study, he/she will be provided with the ICF to review and sign. The ICF includes a detailed explanation of the study design and the potential risks and benefits of treatment. Patients who agree to participate in the study will be provided with a copy of the signed consent form; the original signed consent document will be filed in the patient's medical record. Only eligible and consenting patients will be entered into the study.

Patients will be screened by the site's Investigator or study nurse/coordinate prior to study entry. All patients enrolled on the study will be entered into a patient registration log at each site. Each screened patient will be assigned a sequential patient/study screening number with digits indicating site number and patient study number (e.g., XX-YYY, where XX denotes site number and YYY denotes patient study number as assigned at screening). Original screening records and source documents should be kept for all patients, including those who fail to meet the patient eligibility requirements and any completed eCRFs should be retained for monitoring and auditing. Each patient's data obtained from subsequent evaluations should be recorded and evaluated in the source documents and eCRF. Prior to treatment, the Investigator will re-confirm patient eligibility criteria and assignment of the correct patient study number.

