9.8 Schedules of Events

The study schedule of events is summarized in [Table 5](#), [Table 6](#), [Table 7](#), and [Table 8](#).

Table 5: Study Events Schedule for Cycle 1 (Study Day -14 to Study Day 21): Stage 1 (All Pts) & Stage 2 (AML Pts)

Tests and Observations	Study Day -14 to -4	Study Day -1 to 0	Cycle 1				
			Study Days 1-5 (Up to Study Day 10 if Infusion(s) Held) SL-401 Treatment		Study Day 8±3 ^(q) and 15±3	Study Day 21±7	Study Day 28±7, Then Every 7±3 days
	Screening	Pre-treatment	Pre-Infusion	Infusion		End of Cycle	Delayed End of Cycle for Toxicity Resolution Only if Required
Informed consent form	X						
Inclusion/exclusion criteria	X						
Medical history including prior therapy, concomitant medications	X						
Concomitant Medications		X			X	X	X
ECOG performance status	X					X	X
Physical examination	X	X			X	X	
Pregnancy test ^(a)	X						
Vital signs and weight ^(b)	X	X	X	X	X	X	X
12-lead ECG ^(c)	X	X	X	X (Infusions 1, 5)		X	X
ECHO or MUGA scan ^(d)	X						
Hematology ^(e)	X	X	X		X	X	X
Serum electrolytes ^(f)	X	X	X		X	X	X
Serum albumin ^(g)	X	X	X		X	X	X
Serum chemistry ^(h)	X	X	X		X	X	X
Coagulation parameters: PT/INR, aPTT	X		X		X	X	X
Urinalysis ⁽ⁱ⁾	X		X (Infusion 1)		X	X	X
Tumor response assessment: Bone marrow aspiration ± biopsy ^(j)	X					X	
Tumor response assessment: CT scan ^(k)	X						
Tumor response assessment: Skin, including biopsies and/or photographs ^(l)	X					X	
Tumor response assessment: Peripheral blood						X	
Administration of premeds ^(m)			X				
SL-401 administration ⁽ⁿ⁾				X			
Pharmacokinetic sampling ^(o)			X (Infusions 1, 5)	X (Infusions 1, 5)			
Immunogenicity sampling ^(p)			X (Infusion 1)		X (Day 15)	X	
AE and SAE monitoring			X	X	X	X	X

- (a) Urine or serum pregnancy test must be performed within 1 week prior to treatment in women of childbearing potential.
- (b) Vital signs should be performed after patient is sitting for 3-5 minutes. If during dosing period, vital signs should be taken immediately prior to infusion, immediately after completion of infusion, and 30, 60, and 240 minutes post-infusion.

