10.4 Pregnancy

WOCBP and men with partners of childbearing potential must be using an adequate method of contraception to avoid pregnancy throughout the study and for up to 2 months after the study in such a manner that the risk of pregnancy is minimized. WOCBP include any female who has experienced menarche and who has not undergone successful surgical sterilization (hysterectomy, bilateral tubal ligation, or bilateral oophorectomy) or is not postmenopausal (defined as amenorrhea ≥ 12 consecutive months; or women on hormone replacement therapy with documented serum follicle-stimulating hormone level ≥ 35 mIU/mL). Even women who are using oral, implanted, or injectable contraceptive hormones or mechanical products, such as an intrauterine device or barrier methods (diaphragm, condoms, spermicides) to prevent pregnancy, are practicing abstinence, or whose partner is sterile (e.g., vasectomy), should be considered to be of childbearing potential.

WOCBP must have a negative serum or urine pregnancy test during Screening within 1 week prior to dosing. If the pregnancy test is positive, the patient must not receive study therapy and must not be enrolled in the study.

Sexually active WOCBP must use an effective method of birth control during the course of the study, in a manner such that the risk of failure is minimized.

Prior to study enrollment, WOCBP must be advised of the importance of avoiding pregnancy during study participation and the potential risk factors for an unintentional pregnancy. This information will be included in the ICF that must be signed by the patient.

In addition, all WOCBP or fertile men with partners of childbearing potential should be instructed to contact the Investigator immediately if they suspect they or their partner might be pregnant (e.g., missed or late menstrual period) at any time during study participation.

If following initiation of study treatment, it is subsequently discovered that a patient is pregnant or may have been pregnant at the time of exposure to study therapy, including during at least 2 months after product administration, study therapy will be permanently discontinued in an appropriate manner. Exceptions to discontinuation may be considered for life threatening conditions only after consultation with the Sponsor and Medical Monitor or as otherwise specified in this protocol. The Investigator must immediately notify the Sponsor and Medical Monitor of this event.

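### Protocol 8.10 exempts women on contraception from the pre-treatment pregnancy test that Inclusion 6, Section 10.4 and the schedule tables require of every woman of childbearing potential

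*Protocol*

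**What the plan says.** Protocol Section 8.10 schedules a urine or serum pregnancy test, in the week before treatment, "for WOCBP who are not on acceptable birth control measures".

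The other provisions carry no such restriction:

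- Inclusion 6 (Synopsis and Section 5.2) makes a woman of childbearing potential eligible only if "she has had a negative serum or urine pregnancy test within 1 week prior to treatment".
- Section 10.4 states that "WOCBP must have a negative serum or urine pregnancy test during Screening within 1 week prior to dosing", and that a woman who tests positive may be neither enrolled nor treated.
- Footnote (a) of Table 5 and of Table 7 (Section 9.8) reads "Urine or serum pregnancy test must be performed within 1 week prior to treatment in women of childbearing potential".
- Section 9.1 lists the test at screening for all patients in all stages, with no exemption for contraception.

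Section 10.4 also settles who counts as WOCBP. It names the group that Section 8.10 leaves out, "Even women who are using oral, implanted, or injectable contraceptive hormones or mechanical products", and says that they "should be considered to be of childbearing potential".

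The SAP's Tables 7-1 and 7-3, taken from the Amendment 8 and 9 schedules, repeat the unrestricted footnote.

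**The concern.** Section 8 is where site staff look to see how each procedure is done. A coordinator who reads Section 8.10 alone would conclude that a woman already on contraception needs no test. No later scheduled test would make good the omission, because Tables 6 and 8 have no pregnancy-test row.

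An untested woman who was then dosed would be an eligibility deviation against Inclusion 6. If she were pregnant, the fetus would be exposed to a diphtheria-toxin fusion protein that stops cellular protein synthesis. The rule in Section 10.4 that bars a woman with a positive test protects her only if the test is done.

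The exemption may also be wide. Inclusion 9 has every patient agree to acceptable contraception while on study, and the protocol does not define what is acceptable. A site applying Section 8.10 would be using an undefined standard that could cover many of the women Inclusion 6 is meant to test.

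**Working it through.** The plan gives no figure to reproduce on this point. The check compares the provisions, followed by a rough count of the women concerned.

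**Who must be tested**

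| Provision | Who | Contraception exemption |
|---|---|---|
| Section 8.10 | WOCBP not on acceptable birth control | Yes |
| Inclusion 6, Synopsis | All WOCBP | No |
| Inclusion 6, Section 5.2 | All WOCBP | No |
| Section 10.4 | All WOCBP | No |
| Table 5, footnote (a) | All WOCBP | No |
| Table 7, footnote (a) | All WOCBP | No |

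One statement conflicts with five. The five reduce to three distinct provisions: Inclusion 6 (stated twice), Section 10.4, and footnote (a) (stated twice). Section 9.1 agrees with them. So do the two SAP copies of the footnote, although those are reproductions and not separate requirements.

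**Can the statements be reconciled?** They could be if contraceptive users fell outside WOCBP. Section 10.4 places them inside it, so Inclusion 6 applies to exactly the women whom Section 8.10 exempts.

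**Women concerned, BPDCN**

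- Inputs: about 95 BPDCN patients (Protocol Synopsis, Sample Size), and a male-to-female ratio of about 3.5 to 1 (Protocol 3.1).
- Women: 95 / (3.5 + 1) = 21.1.
- Share who are WOCBP: not in the documents. Protocol 3.1 gives a median age at diagnosis of 66, lower in women. I assume 5% to 30%.
- WOCBP: 21.1 × 0.05 = 1.1, up to 21.1 × 0.30 = 6.3.

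That count spans all stages. Taking only the 44 patients in SAP 3.1 (39 first-line and 5 relapsed/refractory in Stage 4), women number 44 / 4.5 = 9.8. On the same assumption WOCBP number 9.8 × 0.05 = 0.5, up to 9.8 × 0.30 = 2.9. Both counts include every WOCBP, whereas Section 8.10 would exempt only those on contraception. Women with AML are not counted; AML enrolment had closed by Amendment 9.

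**Time under this text.** This version reports the FDA approval of 21 December 2018, and SAP 1.1 ends Stage 4 enrolment on 7 January 2019. That leaves at most 17 days of screening under this exact wording. The wording of Section 8.10 in earlier amendments is not available.

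**The case against.** The strongest reply is that the test is already secured elsewhere. Inclusion 6 is an eligibility criterion, Section 10.4 makes a negative test mandatory before dosing, and Section 9.1 and Table 7 list the test at screening. Pregnancy is itself an exclusion, and Section 8.1 adds that "Prior to treatment, the Investigator will re-confirm patient eligibility criteria". A site would have to overlook all of these. Harm to a fetus would further require that the woman was pregnant despite contraception. Hardly anyone can have been screened under this version, and the patient estimate rests on an assumed share.

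Most of this stands, and it limits the consequence. An untested woman could be dosed only through a site error that Section 8.10 invites, so the harm is possible but not implied. Table 5 governs no new patient, because Stage 1 is complete and AML enrolment is closed. The five statements are three provisions. Inclusion 9 records agreement to use contraception on study and does not show how many women were already using it at screening.

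None of this removes the contradiction. Section 8.10 is an operative procedural instruction, and following it as written produces an Inclusion 6 deviation.

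**Conclusion.** The concern holds. Section 8.10 is wrong as written: it exempts from testing a group that Section 10.4 expressly counts as WOCBP and from whom Inclusion 6 requires a negative test. The textual conflict rests on no assumption.

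Its practical reach is small. About 1 to 6 BPDCN patients across all stages would be WOCBP if the share among women is 5% to 30%, or about 0.5 to 3 among the 44 Stage 4 patients. How many of them were screened under this wording cannot be shown and may be none. Sample size, endpoints and analyses are untouched. The text should be corrected because it concerns safety and eligibility, and because it could be carried into a later protocol.

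**What to change.** In Section 8.10, delete everything after WOCBP in the phrase "for WOCBP who are not on acceptable birth control measures", so that the test applies to all WOCBP within 1 week before treatment. As an option, add the 1-week limit to the pregnancy-test bullet in Section 9.1 so that it matches footnote (a); this is harmonisation only.

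The cost is one deleted clause. No visit is added, and no test beyond the one Inclusion 6 already requires. No schedule cell moves: screening runs from Day -14 to Day -4, so a test on Days -7 to -4 satisfies both windows.

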8.11 Vision Assessment

All patients will be questioned regarding any changes in visual acuity and/or color vision. Patients who have experienced any \geq Grade 2 study drug-related changes in vision (NCI CTCAE v4.03 Grade) will have an ophthalmologic consultation and/or examination performed. In the event any abnormalities are detected, the patient will be followed up as per the recommendations of the consulting ophthalmologist. Management of treatment-related ocular disorders with inflammatory characteristics should include corticosteroid eye drops and/or other measures, as indicated by an ophthalmologist. In the setting of persistent study drug-related ocular disorders \geq Grade 2, consultation with the study's Medical Monitor is required.

8.12 Tumor Assessments and Disease Response Assessment

8.12.1 Stage 1

All patients must have a baseline (pre-treatment) bone marrow aspirate (\pm biopsy) and peripheral blood sample within 14 days prior to the first administration of SL-401. In addition, patients with BPDCN must have a baseline skin assessment (with biopsies and/or for patients with skin involvement) and full-body CT scan within 14 days prior to the first administration of SL-401. Subsequent assessments for response will be performed on the following schedules until, in the judgment of the Investigator, there is evidence of relapsed or progressive disease:

- All patients in Stage 1: bone marrow aspirates (\pm biopsy) 21 (\pm 7) days after the start of Cycles 1 and 2, and thereafter at a schedule determined by the Investigator in consultation with the Sponsor. If the Cycle 1 (Day 21 [\pm 7]) bone marrow examination is empty (i.e., hypocellular) or inadequate, a bone marrow examination should be repeated

in 7 (± 7) days to document response. If additional time is required to complete the repeat examination, consultation with the Medical Monitor is required. If CD123 flow cytometry or IHC stain assessment was performed on the bone marrow aspiration (\pm biopsy), the results should be recorded in the eCRF.

- BPDCN patients: skin assessments (with biopsies and/or photographs for patients with skin involvement) 21 (± 7) days after the start of Cycles 1 and 2 and 21 (± 7) days after the start of every 2nd cycle thereafter (Cycles 4, 6, etc.). CT scans of index lesions 21 (± 7) days after the start of Cycles 2 and 4 and 21 (± 7) days after the start of every 4th cycle thereafter (approximately every 12 weeks).

Tumor response will be assessed by the Investigator using the criteria in [Section 16.1, Appendix A](#) (AML), and [Section 16.2, Appendix B](#) (BPDCN).

8.12.2 Stage 2, Patients with AML

The following disease assessments will be performed at baseline within 14 days prior to the first administration of SL-401 and thereafter for determination of tumor response for patients with AML in Stage 2, as follows. Note that all sites of disease identified at baseline are to be followed thereafter for determination of disease response.

- **Bone marrow aspirates (\pm biopsy)** 21 (± 7) days after the start of Cycles 1 and 2. Patients with evidence of bone marrow involvement prior to study treatment will also have bone marrow evaluations following Cycles 4 and 6 and then every 3 months from Months 6-12; every 6 months from 12 to 24 months; and every 12 months thereafter until there is evidence of relapsed or progressive disease. If the Cycle 1 (Day 21 [± 7]) bone marrow examination is empty (i.e., hypocellular) or inadequate, a bone marrow examination should be repeated in 7 (± 7) days to document response. If additional time is required to complete the repeat examination, consultation with the Medical Monitor is required. If CD123 flow cytometry or IHC stain assessment was performed on the bone marrow aspiration (\pm biopsy), the results should be recorded in the eCRF.
- The Cycle 1-2 Day 21 (± 7 days) bone marrow assessment should occur on Day 21 (± 7 days) even in the setting of patients receiving SL-401 over 6-10 days (as opposed to 5 consecutive days) or in the setting of patients receiving less than 5 doses in a cycle.
- Collection of **peripheral blood samples** for determination of blasts 21 (± 7) days after the start of Cycles 1 and 2. Patients with evidence of peripheral blasts at baseline will also have peripheral blood samples collected 21 (± 7) days after the start of Cycles 1 and 2 and 21 (± 7) days after the start of every 2nd cycle thereafter (Cycles 4, 6, etc.) until there is evidence of relapsed or progressive disease.

Assessment of the anti-tumor activity of SL-401 in patients with AML will be assessed by the Investigator on an exploratory basis using the criteria in [Section 16.1, Appendix A](#).

8.12.3 Patients with BPDCN (Stages 2-4)

A global assessment paradigm is to be followed, with all potential disease sites assessed during screening, including the bone marrow (via aspirate and biopsy), blood (via clinical laboratory testing for blasts and hematologic parameters), skin (via visual examination and photography, with determination of skin disease burden using mSWAT), lymph nodes, liver, spleen, and other viscera (via CT), and lymph nodes, liver, spleen, and other viscera (via physical examination). Positive sites of disease identified during screening must be followed during the study in every response evaluation. (Disease in organs that were disease-positive at screening are to be assessed, documented, and recorded in the clinical database, even if the disease disappeared in subsequent response evaluations.) Sites with no evidence of disease during Screening must be documented as such and an assessment that baseline disease is not present are to be adequately documented in source and recorded in the clinical database; thereafter, these sites need not be followed, unless there is evidence of PD.

The following disease assessments will be performed at baseline within 14 days prior to the first administration of SL-401 and thereafter for determination of tumor response for patients in Stages 2-4, as follows. Note that all sites of disease identified at baseline are to be followed thereafter for determination of disease response.

- **Bone marrow aspirates (\pm biopsy)** samples 21 (± 7) days after the start of Cycles 1 and 2. Patients with evidence of bone marrow involvement prior to study treatment will also have bone marrow evaluations following Cycles 4 and 6 and then every 3 months from Months 6-12; every 6 months from 12 to 24 months; and every 12 months thereafter until there is evidence of relapsed or progressive disease.
 - If the Cycle 1 (Day 21 [± 7]) bone marrow examination is empty (i.e., hypocellular) or inadequate, a bone marrow examination should be repeated in 7 (± 7) days to document response. If additional time is required to complete the repeat examination, consultation with the Medical Monitor is required. If CD123 flow cytometry or IHC stain assessment was performed on the bone marrow aspiration (\pm biopsy), the results should be recorded in the eCRF.
 - The Cycle 1-2 Day 21 (± 7 days) bone marrow assessment should occur on Day 21 (± 7 days) even in the setting of patients receiving SL-401 over 6-10 days (as opposed to 5 consecutive days) or in the setting of patients receiving less than 5 doses in a cycle.
- **Skin assessments**, including photographs, for patients with skin involvement, and determination of skin disease burden using mSWAT (see [Section 16.3, Appendix C](#)) 21 (± 7) days after the start of Cycles 1 and 2 and 21 (± 7) days after the start of every 2nd cycle thereafter (Cycles 4, 6, etc.) until there is evidence of relapsed or progressive disease.

- **Photographs:** Body region(s) where skin lesions are present will be photographed. Digital images/photographs may be collected by the Sponsor or its representatives during routine monitoring visits. Care should be taken to ensure that patients cannot be identified from these images. Refer to the separate Photography Guidelines for detailed photography instructions.
- **Quantification of skin disease burden via the mSWAT:** Quantification of skin disease burden via the mSWAT ([Section 16.3, Appendix C](#)) is required at the time of each skin assessment. Refer to the separate mSWAT Manual for instructions regarding the quantitation of malignant lesions via the mSWAT and response assessment in skin.
- **Skin biopsies:** In situations in which there is substantial reduction of skin lesions (especially when accompanied by disappearance of BPDCN from bone marrow or other sites), a skin biopsy is required. The mSWAT guidance states: “A biopsy of normal appearing skin is unnecessary to assign a complete response. However a skin biopsy should be performed of a representative area of the skin if there is any question of residual disease (persistent erythema or pigmentary change) where otherwise a complete response would exist” ([Olsen et al. 2011](#)).
- **CT scans** of index lesions 21 (± 7) days after the start of Cycles 2, 4 and 6 and 21 (± 7) days after the start of every 4th cycle thereafter (for patients with baseline evidence of lymph node or visceral disease) until there is evidence of relapsed or progressive disease. For patients with no baseline evidence of lymph node or visceral BPDCN involvement, subsequent scans should be performed at the end of Cycle 2 (± 7 days; or at time of disease progression (PD) if PD occurs prior to end of Cycle 2), 21 (± 7) days after the start of Cycle 6, and at Investigator’s discretion thereafter. Baseline CT scans should be full-body (chest/ abdomen/pelvis), whereas follow-up scans should document response of index lesions ([Cheson et al. 2007](#)).
 - During Stages 2-4, subsequent to the end of Cycle 2, imaging at intervals less frequent than those stipulated above may be permitted when required by local regulations; however, this must be reviewed with the Medical Monitor (or designee).
 - For patients in Stages 2-4, electronic copies of all baseline and subsequent CT scans will be submitted to a central archive (scans are to be submitted regardless of the presence/absence of BPDCN-related abnormalities).
- Collection of **peripheral blood samples** for determination of blasts 21 (± 7) days after the start of Cycles 1 and 2. Patients with evidence of peripheral blasts at baseline will also have peripheral blood samples collected 21 (± 7) days after the start of every 2nd cycle thereafter (Cycles 4, 6, etc.) until there is evidence of relapsed or progressive disease.

Tumor response will be assessed by the Investigators for all patients with BPDCN, with the Investigator's assessment to be used in the primary analysis. As a supportive assessment, tumor response was also evaluated by an IRC on a pre-specified subset of patients. Tumor response will be assessed using the Tumor Response Criteria for Patients with BPDCN presented in [Section 16.2, Appendix B](#). All patients will also be followed for DOR and survival until study completion.

[figure not shown]
